2.6.2 Tenofovir 1% Gel

Pharmacokinetics

A Phase 1 Safety and Acceptability Study of the Vaginal Microbicide Agent PMPA Gel, also known as HPTN 050, is a recently completed study of tenofovir vaginal gel with published data.⁸ Eighty-four (60 HIV negative and 24 HIV positive) women applied

either 0.3% or 1% tenofovir gel once or twice daily for 14 days. Systemic absorption was limited (maximum serum levels 3.1-25.8 ng/mL).

Safety

In HPTN 050, the tenofovir 1% gel formulation was well tolerated in both HIV negative and HIV positive women. Although 92% reported at least 1 AE, the majority (87%) were mild and limited to the genitourinary tract (77%). Product concentration, sexual activity and HIV status were not associated with a specific AE pattern. No clinically significant systemic toxicity was observed. Tenofovir gel showed no negative effect on vaginal microflora in this study. No new resistance mutations evolved in plasma or cervicovaginal lavage (CVL) after 14 days of tenofovir gel use but 3 women had plasma mutations associated with low level tenofovir resistance at day 0 and 14 (M41L, L210M, ±T215I/Y). The AE and safety profile in HPTN 050 was reviewed by the FDA who subsequently permitted the initiation of the HPTN 059 extended safety protocol for vaginal tenofovir. Tenofovir gel was highly acceptable to both women and men in HPTN 050, with 94% of the women and 81% of the men indicating that they would definitely or probably use tenofovir gel in the future.

In a male tolerance study of tenofovir 1% gel (CONRAD A04-099) (IND #73,382), tenofovir gel was well tolerated in men following seven days of once daily exposure, for 6 to 10 hours, to the penis. There were few reported and observed genital findings after product use including mild pain (burning, irritation, discomfort) and pruritis². All observed findings were classified as mild, were small in size and required no treatment. All reported symptoms were mild, of short duration and resolved by the final visit. There were no noticeable differences between signs and symptoms of genital irritation observed in the circumcised compared to the uncircumcised group.^{2,9}

A Phase 2 study of tenofovir 1% gel (HPTN 059) has completed follow up. This study assessed safety and acceptability of, and adherence to a regimen of tenofovir gel for vaginal use in HIV-uninfected women versus a placebo gel. Exploratory objectives included measurement of vaginal flora characteristics, assessment of the effects of gel on genital cytokine and chemokine expression, and the evaluation of cytokine and chemokine expression with evidence of inflammation, epithelial disruption and genital symptoms. The study was a Phase 2 four arm, three site, randomized, controlled trial comparing gel used once daily and gel used prior to intercourse, to placebo gel, with 6 months gel exposure and follow-up. The study was conducted among 200 women in Pune, India; Birmingham, Alabama, USA; and New York, New York, USA. Participants were sexually active, HIV-uninfected women between ages 18 and 50, but not menopausal or post menopausal. Participants had six months of study gel exposure and six months of follow-up. They were randomized to either once daily or coitally dependent group, and received either tenofovir or placebo gel. Participants received single use unit dose tubes and single use applicators.

No statistically significant differences were seen between those receiving active and placebo gels in complete blood count, liver function tests, or renal function tests. Among those using a study gel daily, no participants had pelvic exam findings involving

generalized erythema or severe edema or deep epithelial disruption at any follow-up visit during the study. At the Week 24 Visit, no participants had exam findings suggestive of vaginitis, cervicitis, superficial disruption, disrupted blood vessels, or intermenstrual bleeding. Adherence to study gel was high, and was supported by PK data. 79% of women reporting gel use in past 12 hours had low but detectable plasma tenofovir supporting self-reported adherence data. Daily and coital use was highly acceptable to women. These data suggest a favorable safety and acceptability profile of tenofovir gel, and support routine monitoring for genital findings among women without genital symptoms at six month intervals.¹⁰

Several other tenofovir gel studies are ongoing or in development. These include:

- CONRAD A04-095: Single Dose and 14-Day Once or Twice-daily Pharmacokinetic Study of the Vaginal Microbicide Agent 1% Tenofovir Gel (IND #73,382)
- CAPRISA 004: Safety and Effectiveness Study of a Candidate Vaginal Microbicide for Prevention of HIV (proposed Phase 2B, two-arm, double-blinded, randomized, placebo controlled trial comparing 1% tenofovir gel with a placebo gel)
- MTN-002: Phase 1 Study of the Maternal Single-Dose Pharmacokinetics and Placental Transfer of Tenofovir 1% Vaginal Gel among Healthy Term Gravidas
- MTN-003: Phase 2B Safety and Effectiveness Study of Tenofovir 1% Gel, Tenofovir Disoproxil Fumarate (TDF) Tablet and TDF-Emtricitabine Tablet for the Prevention of HIV-1 Infection in Women
- MTN-006: Phase 1 Rectal PK Study of Tenofovir 1% Gel
- MTN-007: Phase 1 Rectal Safety of Tenofovir 1% Gel

2.7 Study Hypothesis and Rationale

2.7.1 Study Hypothesis

MTN-001 hypothesizes that:

- There will be no differences in rates of adherence among the three study regimens
- There will be no difference in rates of acceptability among the three study regimens
- Tissue levels of PMPA will be similar irrespective of the route of administration

- Oral TDF will be associated with higher concentrations of PMPA in the blood compared to topical administration of PMPA
- Neither tenofovir 1% gel nor oral TDF regimens will adversely impact the genital tract environment

2.7.2 Rationale

Adherence

The microbicide field will benefit from evaluating the behavioral factors associated with adherence to oral and vaginal formulations. The full complement of HIV prevention strategies in the future may include orally or vaginally formulated agents or combinations of both. Accordingly, efficacy trials should also include regimens of oral, vaginal, or both types of formulations. Different strategies will likely appeal to different risk populations, or even to the same woman at different times in her life. A woman's level of adherence to a particular prevention modality would impact its effectiveness, depending on her use pattern and the drug's half-life, as well as its effect (if any) on her health. It has also been posited that different levels of adherence to PrEP or ARV-based vaginal microbicide use could have variable effects on the development of drug-resistant virus in a woman unknowingly infected with HIV.

Understanding how product formulation affects adherence and acceptability as well as sexual risk taking (particularly condom use) is important to the design of the MTN-003 trial. Including adherence and acceptability assessments in MTN-001 permits the opportunity to pilot measures that would be used in MTN-003. Behavioral adherence data could complement interpretation of PK results.

Pharmacokinetics

No head to head comparison controlling for intra-individual variability has yet been performed to compare the relative efficiency of oral versus vaginal tenofovir dosing to achieve measurable and "adequate" (biologically active based on *in vitro* data) tenofovir levels in tissue. MTN-001 will evaluate intracellular tenofovir diphosphate concentrations (active moiety) in tissue and blood to inform PK models.

Based on data from HPTN 050, only one-third of the participants are expected to yield measurable levels in blood after vaginal dosing of tenofovir gel. An intensive PK sampling cohort is planned to provide frequent blood samples and carefully timed corresponding cervicovaginal lavage (CVL) and vaginal biopsy, one per woman, at pre-specified times after dosing to provide data for a sparse sampling analysis. For this reason and for reasons of technical capacity, all participants at the United States (US) sites will enter the Intensive PK substudy.

2.8 Justification of Dosing

Tenofovir 1% Vaginal Gel

Choice of the tenofovir 1% vaginal gel concentration for MTN-001 is based on both animal and clinical evidence suggesting an appropriate safety profile and potency. Animal and human studies have demonstrated minimal vaginal irritation at this concentration. A rabbit vaginal irritation test identified tenofovir 1% gel as being histopathologically identical to sham or control treatment, while on a qualitative basis 3% gel was more irritating to vaginal epithelia.² The tolerability of the 1% gel was confirmed in the HPTN 050 Phase 1 study, the Phase 1 dose ranging study of tenofovir gel (0.3% once daily, then 1.0% once daily, then 0.3% twice daily followed by 1% twice daily).^{2,Error! Bookmark not defined.} In this study, of the two doses and frequencies studied in the dose finding cohort, the 1% gel applied intravaginally twice daily for 14 days was well tolerated and was identified as the highest practical dose and frequency for further study in subsequent cohorts.

The second line of evidence is from vaginal transmission inhibition studies performed in non-human primates.² Six separate studies provided evidence for efficacy of the gel over a range of tenofovir concentrations of 1% to 10%. Although the total data are limited and a powered statistical determination as to the efficacy of tenofovir 1% gel versus 0.3% and 10% cannot be made, empirical examination of the efficacy data identifies tenofovir 1% gel as the lowest efficacious concentration tested when given within two hours of infection.

Finally, limited vaginal PK tenofovir data in primates demonstrate that tenofovir gel is broadly distributed in vaginal tissues following vaginal application and can penetrate to epithelial tissues.¹¹ The amount of tenofovir administered by intravaginal application of 4 grams of a 1% dose (40 mg) is highly active against HIV and results in a reduction of plasma HIV ribonucleic acid (RNA) of 1.5 log₁₀ copies / mL after daily administration for 21 days. Comparison of the predicted cervicovaginal concentrations of tenofovir gel delivered to those achieved systemically at the standard treatment dose of 300 mg TDF, and tenofovir's characteristic prolonged intracellular half-life (diphosphate form, nine to 50 hours depending upon cell type), suggest that an initial and potentially durational barrier to HIV transmission may be possible. In terms of weighing potential risks and benefits, the tenofovir 1% gel minimizes the potential risks of vaginal epithelial toxicity while providing the potential benefit of delivering sufficient tenofovir to achieve an initial and possibly durational barrier to infection.

Tenofovir Disoproxil Fumarate 300 mg Tablets

Choice of the 300 mg strength of the TDF tablet is based upon practical and scientific considerations. The TDF 300 mg tablet, or Viread[®], is the medication US FDA approved for the indication of treatment of HIV-1 infection. More than 12,000 people have been treated with TDF alone or in combination with other antiretroviral medications for periods of 28 days to 215 weeks in Phase 1–3 clinical trials and expanded access studies. A total of 1,544 patients have received TDF 300 mg once daily in Phase 1–3 clinical trials and over 11,000 people have received TDF in expanded access studies. A

significant body of safety data has been accumulated for daily use of the TDF 300 mg tablet. In addition, data on tenofovir PK and anti-viral activity in humans suggest a reasonable expectation of effectiveness as a prevention strategy.

3 OBJECTIVES

3.1 **Primary Objectives**

- To compare adherence to and acceptability of three daily regimens of tenofovir (oral, vaginal, and dual use)
- To compare systemic and local PK among three regimens of tenofovir (oral, vaginal, and dual use) in a subset of participants

3.2 Secondary Objectives

- To identify factors associated with product adherence, and whether these differ when women use one of three daily regimens of tenofovir (oral, vaginal, and dual use)
- To examine whether sexual activity or male condom use varies when women use one of three daily regimens of tenofovir (oral, vaginal, and dual use)
- To assess the timing of product use with sexual intercourse
- To determine the level of sharing of study products with non-participants (and to assess with whom products are shared)
- To characterize the differential safety profiles of three daily regimens of tenofovir (oral, vaginal, and dual use)

3.3 Exploratory Objectives

- To build a PK model of intracellular-extracellular tenofovir levels in the systemic and female genital tract compartments
- To examine the impact of oral and vaginal tenofovir gel on mucosal immunity in the female genital tract
- To assess correlation of PK and adherence measures

4 STUDY DESIGN

4.1 Identification of Study Design

MTN-001 will be a Phase 2, multi-site, randomized, six sequence, three period open label crossover study of adherence to and PK of TDF 300 mg tablet and tenofovir 1% gel.

4.2 Summary of Major Endpoints

- Participant self-reported product use. For each woman, adherence to each regimen will be computed by dividing the number of daily doses she reports having taken (numerator) by the number of expected doses if she were fully adherent (denominator).
- The proportion of participants who indicate they would be "unlikely" to use the study product in the future.
- AUC, C_{max}, and C_{min} associated with oral, vaginal, and dual use regimens.

4.3 Description of Study Population

The study population will include approximately 144 evaluable generally healthy 18-45 year-old women who are HIV-uninfected, non-pregnant, sexually active and using adequate contraception, as described in Section 5.2. Among the total approximately 144 evaluable participants, the 72 participants enrolled at all US study sites will undergo more intensive specimen collection for PK analysis. These participants are hereafter referred to as "Intensive PK participants."

4.4 Time to Complete Enrollment

The approximate time to complete study enrollment is expected to be six months. The time of total study duration is expected to be a minimum of approximately one year, including the study follow-up period.

4.5 Study Groups

Six study sequences are planned. The 144 planned participants will be randomized equally across all 6 sequences in a 1:1:1:1:1 ratio. All study participants will be assigned to complete each study period (oral, gel, oral plus gel) once in an order that will be randomly assigned. Up to 204 women may be enrolled to reach the target of 144 evaluable women (i.e., women who have at least one follow-up visit with adherence data in each of the three periods of the study). The need to enroll replacement participants for enrollees will be dependent on whether the enrollee had at least one full period of the study with no follow-up adherence data. Details on procedures for

participant replacement are outlined in the MTN-001 Study Specific Procedures (SSP) Manual (www.mtnstopshiv.org).

4.6 Sequence and Duration of Trial Periods

The total duration of participation from the Enrollment Visit to the Termination Visit is 21 weeks, including three six-week study periods and three one-week washout periods. Visits may be completed within specified windows around target dates. Detailed information regarding visit windows will be thoroughly described in the MTN-001 SSP Manual.

4.7 Expected Duration of Participation

The expected duration of participation for individual enrolled participants is 21 weeks. No study data will be collected after the 21-Week Termination Visit unless the participant has an AE that has not resolved or stabilized, or is pregnant at the Termination Visit, or is a participant in the in-depth interview with applicable characteristics described in Section 7.6.

Participants who have AEs at the Termination Visit that have not resolved or stabilized will be followed beyond the Termination Visit until a clinically acceptable resolution of the AE(s) is confirmed and documented. Clinical acceptability of resolution will be determined by the site IoR in consultation with the Protocol Safety Review Team (PSRT). For participants who are pregnant at the Termination Visit, study site staff will make every effort to follow the participant until such time that her pregnancy outcome can be ascertained and documented.

4.8 Sites

Seven study sites are planned for this trial:

- Umkomaas CRS, Durban, KwaZulu-Natal, South Africa
- Botha's Hill CRS, Durban, KwaZulu-Natal, South Africa
- Makerere University JHU Research Collaboration {MUJHU CARE LTD} CRS, Kampala, Uganda
- Alabama Microbicide CRS, Birmingham, USA
- Bronx-Lebanon Hospital Center, Bronx, USA
- Case CRS, Cleveland, USA
- Pitt CRS, Pittsburgh, USA

5 STUDY POPULATION

5.1 Selection of the Study Population

The inclusion and exclusion criteria outlined in Sections 5.2 and 5.3 will be utilized to ensure the appropriate selection of study participants for MTN-001.

5.1.1 Recruitment

Participants will be recruited from family planning and other health clinics, colleges, and other venues. Site IRB-approved media advertisements, telephone scripts, and fliers may be used.

5.1.2 Retention

Each site will establish participant retention procedures. Study site staff members at each site are responsible for developing and implementing site-specific standard operating procedures (SOPs) to target high rates of retention. Further information on retention of participants is provided in Section 10.6.

5.1.3 Enrollment Guidelines

Women with participation in any other investigational drug or device trial in the 30 days prior to enrollment will not be enrolled in this study. Study participants will be required to refrain from enrollment in other clinical trials involving investigational or prohibited drugs or investigational devices during their involvement in this study. Participants who report after enrollment their concurrent participation in such trials will be discussed by the PSRT and may be discontinued from use of study product(s). In this case they will be encouraged to remain in the study and will be followed with all safety evaluations deemed clinically appropriate by the Investigator and the NIH medical officer.

5.2 Inclusion Criteria

Women must meet all of the following criteria to be eligible for inclusion in the study:

- 1) Age 18-45 years (inclusive) at screening, verified per site SOP
- 2) Willing and able to provide written informed consent for screening and enrollment
- 3) Willing and able to provide adequate locator information, as defined in site standard operating procedures
- 4) HIV-uninfected based on testing performed by study staff during screening procedures (per applicable algorithm in Appendix II)

- 5) In general good health at screening and enrollment, as determined by the site IoR or designee
- 6) Per participant report at screening, usual menstrual cycle with at least 21 days between menses (does *not* apply to participants who report using a progestin-only method of contraception at screening, e.g., Depo-Provera)
- 7) Calculated creatinine clearance at least 70 mL/min by the Cockcroft-Gault formula where creatinine clearance (female) in mL/min = (140 - age in years) x (weight in kg) x 0.85/72 x (serum creatinine in mg/dL)
- 8) Per participant report at screening, sexually active, defined as having had penilevaginal intercourse at least four times in the four weeks prior to screening
- 9) Per participant report at screening and enrollment, intending to continue penilevaginal intercourse at least once per week for the duration of study participation
- 10) Per participant report at enrollment, use of an effective method of contraception at enrollment, and intending to use same method for the duration of study participation and one month thereafter; effective methods include hormonal methods (except vaginal ring); intrauterine contraceptive device (IUCD) inserted at least 30 days prior to enrollment; and sterilization (of participant or her sexual partner or partners as applicable, self-report acceptable)
- 11) Normal Pap smear result at screening or adequately documented normal Pap smear result per SSP within the 12 calendar months prior to screening
- 12) At screening and enrollment, agrees not to participate in other research studies involving drugs, medical devices, or vaginal products for the duration of study participation

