The behavioral factors associated with adherence to different prevention strategies are still being described. The full complement of HIV prevention strategies in the future arguably could include both orally and vaginally formulated agents. Different strategies will likely appeal to different risk populations, or even to the same woman at different times in her life. A woman's adherence to a particular prevention strategy would impact its effectiveness, as well as its effect on her health. Different levels of adherence to PrEP or ARV-based vaginal microbicide use could also have variable effects on the development of drug-resistant virus in a woman unknowingly infected with HIV. Thus, understanding how and why women are willing or able to commit to a particular formulation is vital to the development of safe and effective drug-based prevention strategies.

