7 STUDY PROCEDURES

An overview of the study visits and evaluations schedule is presented in Appendix I. Presented in this section is additional information on visit-specific study procedures. A detailed instruction guide will be provided in the MTN-001 SSP Manual.

In addition to any Interim Visits that may occur in accordance with guidance outlined in Section 7.5, the following visits should take place for study participants:

- Screening
- Enrollment (Period 1 Start)
- 3-Week Visit (Mid-Study-Period Visit)
- 6-Week Visit (Period 1 End)
- 7-Week Visit (Period 2 Start)

- 10-Week Visit (Mid-Study-Period Visit)
- 13-Week Visit (Period 2 End)
- 14-Week Visit (Period 3 Start)
- 17-Week Visit (Mid-Study-Period Visit)
- 20-Week Visit (Period 3 End)
- 21-Week Visit (Termination Visit)

Participants will be in an oral dosing period, vaginal dosing period, and dual dosing period, once each (with the order depending on randomization) during the three six-week study periods (Study Period 1, Study Period 2, and Study Period 3). The Enrollment Visit will be considered Day 0 and will occur no more than 30 days following provision of informed consent for screening. The 3-Week, 10-Week, and 17-Week Visit are at the approximate midpoints of Study Periods 1, 2, and 3. These three visits will all follow the format of the Mid-Study-Period Visit. Each of the three study periods is followed by a one-week washout period. These washout periods are between the 6-and 7-Week Visit, the 13- and 14-Week Visit, and the 20- and 21-Week Visit.

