7.1 Screening Visit

After providing written informed consent, potential participants may be screened for eligibility over two or more visits if necessary, and eligibility must be confirmed at the enrollment visit. For participants who do not meet the eligibility criteria, screening will be discontinued when ineligibility is determined.

For participants who are found to be presumptively eligible based on the evaluations listed below at these visits, final eligibility will be confirmed at the Enrollment Visit, scheduled to take place within 30 days of the initial Screening Visit. Unless otherwise specified in the protocol or MTN-001 SSP Manual, laboratory testing for the purpose of determining eligibility will occur prior to (and does not include testing during) the Enrollment Visit.

Table 4: Screening Visit

Screening Vis	sit (up to 30 days prior to Enrollment Visit)
Component	Procedure/Analysis
Administrative	 Obtain written informed consent for screening Assign Participant ID (PTID) Collect demographic information Collect locator information Assess behavioral eligibility Provide reimbursement for study visit Schedule next visit
Clinical	 Collect medical/menstrual history Collect concomitant medications Perform physical exam (See Appendix III) Perform pelvic exam (See Appendix III) Provide counseling Contraceptive HIV pre- and post-test HIV/STI risk reduction and male condom *Treat for UTI/RTIs/STIs, treat or refer for other findings Provide male condoms
Urine	 Collect urine sample Qualitative hCG Dipstick UA (*and culture if positive for leukocyte esterase or nitrates; may omit if culture not standard of care for UTI diagnosis) SDA for chlamydia and gonorrhea
Blood	 Collect blood samples Complete blood count Liver function tests Serum chemistries Syphilis serology (confirmatory tests as needed) HIV-1 test (confirmatory tests as needed) HBsAg
Pelvic	 Collect pelvic samples Vaginal pH Vaginal fluid for wet mount (BV, Candida, Trichomonas) *Herpes culture (at sites where standard of care for diagnosis) **Pap smear

*If indicated (see also MTN-001 SSP Manual) **If no documented normal pap result within 12 months of screening is available.

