7.2 Enrollment Visit

Table 5: Enrollment Visit

Enrollment Vi	sit (Study Period 1 Start)
Component	Procedure/Analysis
Administrative	 Obtain written informed consent for enrollment (incl. compr. checklist) Review/update locator information Confirm behavioral eligibility, required for eligibility assessment Schedule next study visit Provide reimbursement for visit Follow procedures for randomization assignment
Clinical	 Update medical/menstrual history, required for eligibility assessment Update concomitant medications, required for eligibility assessment Document pre-existing conditions, required for eligibility assessment Perform physical exam (See Appendix III), required for eligibility assessment Perform pelvic exam (See Appendix III), required for eligibility assessment Perform pelvic exam (See Appendix III), required for eligibility assessment *Treat for UTI/RTIs/STIs, treat or refer for other findings Provide counseling Contraceptive *HIV pre- and post-test HIV/STI risk reduction and male condom Protocol adherence, product use/adherence
Behavioral	Administer baseline behavioral assessment
Urine	 Collect urine sample Qualitative hCG, required for eligibility assessment *SDA for chlamydia and gonorrhea *Dipstick UA (*and culture if positive for leukocyte esterase or nitrates; may omit if culture not standard of care for UTI diagnosis)
Blood	 Collect blood specimens Complete blood count (not for eligibility assessment) Liver function tests (not for eligibility assessment) Serum chemistries (not for eligibility assessment) *Syphilis serology (confirmatory tests as needed) *HIV-1 test (conf. tests as needed) (per standard in site SOP) Plasma for storage
Pelvic Samples	 Collect vaginal pH Collect vaginal fluid for wet mount (BV, Candida, Trichomonas) Collect CVL for vaginal flora proteomics and markers of inflammation *Collect herpes culture (at sites where standard of care for diagnosis)
Study Product Supply	Appropriate number of doses of study product(s)

*If indicated (see also MTN-001 SSP Manual)

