APPENDIX II: HIV ANTIBODY TESTING ALGORITHMS

Algorithm for HIV antibody testing – Screening (and Enrollment if applicable)

Algorithm for HIV antibody testing during follow-up

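### HIV-negative status is required only at screening, up to 30 days before randomisation, so an infection detectable at enrollment may go unseen for up to 6 weeks of tenofovir

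*Protocol*

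**What the plan says.** Section 5.2, item 4, sets the entry standard: the woman must be "HIV-uninfected based on testing performed by study staff during screening procedures (per applicable algorithm in Appendix II". Enrollment is not named. Section 7 places Day 0 at the Enrollment Visit, which "will occur no more than 30 days following provision of informed consent for screening".

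The screening table (Table 4) lists "HIV-1 test (confirmatory tests as needed" without condition. The enrollment table (Table 5) lists "HIV-1 test (conf. tests as needed) (per standard in site SOP" with an asterisk, which its footnote ties to an indication and to the SSP Manual. The pregnancy test in the same table reads "Qualitative hCG, required for eligibility assessment"; the HIV line carries no such mark.

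Section 7.1 adds that "laboratory testing for the purpose of determining eligibility will occur prior to (and does not include testing during) the Enrollment Visit", subject to an exception where the protocol or the SSP Manual says otherwise. Appendix II is headed "Algorithm for HIV antibody testing – Screening (and Enrollment if applicable"; the algorithm itself is a figure that was not available to this review.

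Appendix I agrees. The HIV-1 test is fixed at screening, conditional at enrollment, and fixed at weeks 7, 14 and 21, with none at weeks 3 or 6. Once infection is identified, section 9.6 ends all study product for good, and section 7.4.1 ends product supply and PK assessments.

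**The concern.** The protocol names the hazard itself. Section 2.1 raises possible effects on "the development of drug-resistant virus in a woman unknowingly infected with HIV", section 2.7.2 repeats the point, and section 13.3.1 mentions a theoretical risk of mutation in participants who become infected during the study. All three regimens supply only tenofovir gel, TDF tablets or both, with no second antiretroviral.

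Exposure continues while eligibility is being settled. Section 5.2 requires at least four sex acts in the four weeks before screening and an intention to continue weekly. Section 5.3, item 7, lets a woman with a treatable sexually transmitted infection at screening enroll once treated and symptom-free within the 30 days, without requiring a repeat HIV test.

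Pregnancy and HIV infection both lead to permanent discontinuation of all product (sections 9.6 and 9.7), yet only pregnancy must be re-checked before the first dose. Whether HIV is re-checked can differ among seven sites in three countries. At stake are avoidable single-drug exposure during unrecognised infection and, for each such woman, the loss of on-product data in periods 2 and 3.

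**Working it through.** **Schedule.** Inputs: up to 30 days from screening consent to Day 0 (section 7); 6 weeks on product then 1 week of washout (section 6.1); last dose of a period given under observation at the end-of-period visit (section 6.4.2.1); washout between weeks 6 and 7 (section 7); next HIV test at week 7 (Table 8, Appendix I).

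- Check on the protocol's own figure: 3 × (6 + 1) = 21 weeks, the stated follow-up.
- Day 0 to the next scheduled HIV test: 7 × 7 = 49 days.
- On product within that interval: 6 × 7 = 42 days. The last 7 days are washout.
- Longest gap between required HIV tests: 30 + 49 = 79 days.
- With a required Day 0 test: 49 days. An infection that this test misses could still meet up to 42 days of product.

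These are target-date figures; visit windows are left to the SSP Manual.

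**Expected number of women.** The protocol gives no HIV incidence, so 1 to 6 per 100 person-years is an assumption. Formula: women × gap in days / 365 × incidence.

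- Ceiling, with maximum enrollment (section 10.6) and the full gap: 204 × 30/365 = 16.8 person-years; × 0.01 to 0.06 = 0.17 to 1.0.
- 144 women, full gap: 144 × 30/365 = 11.8 person-years; 0.12 to 0.71.
- 204 women, assumed mean gap of 15 days: 204 × 15/365 = 8.4 person-years; 0.08 to 0.50.
- As the previous line, but with only the non-US half (102 women) at that risk: 4.2 person-years; 0.04 to 0.25.

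Women already in the antibody window at screening should not be added to these counts. At constant incidence, the number who become detectable between screening and Day 0 is about incidence × gap, whatever the length of the window. The figures above therefore already approximate what a Day 0 test would find.

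**The case against.** The strongest reply is that the sections agree with one another and look deliberate. Screening results decide most laboratory criteria: creatinine, liver function, phosphate, hemoglobin, platelets and HBsAg are all judged at screening (section 5.3, item 4), and HBsAg is not listed at enrollment at all. On that view the pregnancy test is the exception. This stands, so a reader who infers an internal contradiction goes too far. The pregnancy comparison shows only that the protocol can require a Day 0 result where it wants one.

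Second, a Day 0 HIV test may in practice be done. The SSP Manual, a site procedure or a clinical indication can each trigger it, and the algorithm was not available to this review. A reader might infer that such infections will go unseen; the documents support only that they may.

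Third, a reader might take the week-7 test to mean 7 weeks on drug. It does not: product ends at the week-6 visit.

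Fourth, the consequences are easy to overstate. Section 8.3.2 does not list HIV infection as a serious adverse event in itself. Sequences B and F, a third of women, begin on gel alone, for which section 2.6.2 reports limited systemic absorption. Condoms and risk-reduction counseling are given at screening. Women without adherence data for a full period can be replaced (section 10.6), so the effect on the trial's comparisons is negligible.

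None of this removes the gap in the entry criterion. Site-dependent testing is a weak guard for a hazard that the protocol itself raises. The plasma stored at enrollment could date an infection afterwards but would not prevent exposure.

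**Conclusion.** The point holds as a weakness in an entry criterion. The only HIV test required for entry is at screening. Unless the SSP Manual or a site procedure adds one at Day 0, a woman with detectable infection at enrollment may receive up to 42 days of tenofovir as her only antiretroviral. Her next scheduled test comes up to 79 days after her last required one, and she would then have no product or PK assessments in periods 2 and 3.

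The numbers are small. The ceiling is about 0.2 to 1.0 infections, or about half that with a 15-day mean gap. Both rest on an assumed incidence of 1 to 6 per 100 person-years and on 204 enrollees. The case for change is participant safety at low cost, not any effect on power or on the primary comparisons.

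**What to change.** - Restate inclusion criterion 4 as HIV-uninfected at screening and at enrollment.
- In Table 5, remove the asterisk and the reference to site procedure from the HIV-1 test, and mark it as required for eligibility, as the pregnancy test is. Make the linked pre- and post-test counseling unconditional.
- In Appendix I, replace the asterisk for the HIV-1 test and its counseling at enrollment with a fixed entry.
- State that the rapid-test result must be available before randomisation.

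The general rule in section 7.1 can stay, because it already yields where the protocol specifies otherwise.

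The cost is one rapid test with counseling per enrollee (up to 204) and a somewhat longer enrollment visit. Blood is already drawn at that visit, section 7.9.1 already allows rapid tests, and Appendix II already provides for enrollment testing. The longest gap between required tests falls from 79 to 49 days. The change does not help a woman whose infection is still undetectable at Day 0.
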